## **2.2 ENDPOINTS**

### **2.2.1 Primary Endpoint**

The primary endpoint will be the degree and location of platelet activation as determined by the target to background ratio of F-GP1.

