## **3 STUDY DESIGN**

This will be a prospective observational case-control cohort study

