## **4 STUDY POPULATION**

### **4.1 NUMBER OF PARTICIPANTS**

We will recruit two patient populations after invasive coronary angiography has been completed. We have established comparator control populations including 50 patients with stable coronary artery disease (no angina or recent myocardial infarction) and valvular heart disease who underwent F-GP1 cardiac PET-CT as part of a concurrent study (NCT04073875) (34).

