## 9 STATISTICS AND DATA ANALYSIS

### 9.1 SAMPLE SIZE CALCULATION

We have found that  $^{18}\text{F}$ -GP1 is markedly discriminatory for the presence of thrombus with an accuracy of 96% with 100% specificity and false negatives predominantly seen in patients imaged beyond 7 days from presentation (37). The prevalence of coronary thrombosis in patients with myocardial infarction and non-obstructive coronary arteries is unknown but estimates suggest that plaque disruption may be as high as one third of cases although it is unclear if this is bystander disease or the cause of the infarction (19). We have estimated that routine clinical evaluation may suggest thrombus in 10-20% of patients with myocardial infarction and non-obstructive coronary arteries. For 80-90% power at two-sided  $p < 0.05$ , we will require a study population of 36-50 to detect an incidence of thrombosis of 25-40%. Population sizes for coronary thromboembolism and spontaneous coronary dissection are based on the proof-of-principle of the detection of coronary thrombosis and have greater than 95% power to detect a prevalence of coronary thrombus in over two thirds of patients.

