### 9.2 PROPOSED ANALYSES

As with our previous studies, image analysis will be performed on bespoke PET analysis software from our long-standing collaborators (FusionQuant, Cedars Sinai Hospital, Los Angeles) that provides automated motion correction and advanced cardiovascular PET quantification (31, 32, 38). After accurate co-registration of the PET and CT data sets,  $^{18}\text{F}$ -GP1 uptake will be quantified within regions of interest around areas of thrombus on the CT images.

Descriptive statistics will incorporate numbers and proportions, means and standard deviations or median and interquartile ranges. Proportions will be compared with Chi-squared test and continuous variables will be compared with regression analysis, Student's *t*-test or analysis of variance with repeated measures for longitudinal assessments. Statistical significance will be taken as two-sided  $p < 0.05$ .

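### Section 9.2 names the pooled-variance t-test with no unequal-variance version; comparing TBR in a group of 10 with the 50 controls could then overstate precision

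*Protocol*

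**What the plan says.** Section 9.2 gives one general sentence on comparing continuous measurements: "continuous variables will be compared with regression analysis", "Student's *t*-test or analysis of variance with repeated measures for longitudinal assessments". Student's t-test is the only method there that is specific to two groups, and it pools the variance. Medians and interquartile ranges are allowed for description, but no unequal-variance, rank-based or robust comparison is named. The section ends with "Statistical significance will be taken as two-sided" p<0.05 and does not mention confidence intervals.

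The primary endpoint (2.2.1) is "the degree and location of platelet activation as determined by the target to background ratio of" 18F-GP1, a continuous quantity. Section 3 calls the design a "prospective observational case-control cohort study". Section 4.1 gives the comparators as "50 patients with stable coronary artery disease (no angina or recent myocardial infarction) and valvular heart disease". Section 4.1.1 plans 50 patients in Cohort 1, and 4.1.2 plans three groups of 10 in Cohort 2. Section 9.1 says that the thromboembolism and spontaneous dissection groups "have greater than 95% power to detect a prevalence of coronary thrombus in over two thirds of patients".

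**The concern.** The pooled t-test assumes the same variance in both groups. It tolerates a violation when the groups are of equal size, but not when the smaller group has the larger variance: the pooled estimate is then dominated by the larger, tighter group and the standard error comes out too small.

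The protocol's own expectations point that way. Section 1.1.5 reports tracer uptake confined to culprit arteries, and 9.1 reports 100% specificity, so controls should lie near background. If roughly two thirds of a group of 10 take up tracer and the rest do not, TBR in that group is a mixture, and a mixture spreads more widely than its background component. At stake is the stated precision of any comparison of mean TBR or SUV between a group of 10 and the 50 controls.

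**Working it through.** **Inputs.** From the protocol: group sizes 10, 50 and 50 (4.1); thrombus in over two thirds of two of the groups of 10, and in 25-40% of Cohort 1 (9.1). Not in the protocol: any TBR mean or SD. Those below are assumptions.

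**The plan's own figures.** Section 9.1 sizes on proportions. For one proportion, n = [(1.96·√(p0·q0) + z·√(p1·q1))/(p1 − p0)]² with p0 = 0.20 and p1 = 0.40 gives 36 at 80% power and 50 at 90%, which reproduces the stated 36-50. For n = 10 and a prevalence of 2/3, exact one-sided 0.025 binomial power is 99.7% against a null of 5% and 98.0% against 10%, so the claim of more than 95% holds at those nulls (it is 78.7% against 20%). None of this says anything about the spread of TBR.

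**Step 1: standard error.** Let k be the case SD divided by the control SD, with 10 cases and 50 controls.
- Pooled SE² = [(9k² + 49)/58]·(1/10 + 1/50)
- True SE² = k²/10 + 1/50

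At k = 2: pooled (85/58)·0.12 = 0.176, true 0.420, ratio of SEs √(0.176/0.420) = 0.65.

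| k | pooled SE / true SE | Student coverage of nominal 95%, normal data |
|---|---|---|
| 1 | 1.00 | 95% |
| 1.5 | 0.77 | 87% |
| 2 | 0.65 | 80% |
| 3 | 0.54 | 71% |
| 5 | 0.47 | 64% |

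With 50 against 50 the SE ratio is 1.00 at every k and coverage stays at about 95%.

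**Step 2: what k a mixture produces.** With share p positive and separation s, the case variance is p·SD₊² + (1 − p)·SD₋² + p(1 − p)·s². For p = 2/3, s = 0.5, SD₊ = 0.2 and SD₋ = control SD = 0.1: 0.0267 + 0.0033 + 0.0556 = 0.0856, so the SD is 0.29 and k is 2.9.

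**Step 3: simulated mixtures** (10 v 50, p = 2/3, 40,000 runs each).

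| s, SD₊/SD₋ | k | Student coverage | Welch coverage | Power, Student / Welch |
|---|---|---|---|---|
| 0.2, 0.2/0.2 | 1.1 | 93% | 95% | 46% / 37% |
| 0.2, 0.1/0.1 | 1.4 | 88% | 95% | 90% / 74% |
| 0.5, 0.2/0.2 | 1.5 | 86% | 95% | 96% / 82% |
| 0.3, 0.15/0.1 | 2.0 | 80% | 95% | 97% / 81% |
| 0.5, 0.2/0.1 | 2.9 | 71% | 95% | 99.6% / 90% |
| 1.0, 0.4/0.2 | 2.9 | 71% | 95% | 99.6% / 90% |
| 1.0, 0.3/0.1 | 5.3 | 64% | 94% | 99.9% / 95% |

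In the fifth row the median half-width is 0.10 for Student and 0.21 for Welch. If all 10 are positive (0.5, 0.2/0.1) there is no mixture but k is still 2, and Student covers 79%. Welch is not exact everywhere: with 80% positive and a separation of 8 control SDs it covers 89%, against 68% for Student.

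**Step 4: the other comparisons.** Cohort 1 against the controls (50 v 50, 25-40% positive): both methods cover 94-95%. A group of 10 against Cohort 1: at s = 0.5 and SDs 0.2/0.1, Cohort 1 has variance 0.25·0.04 + 0.75·0.01 + 0.1875·0.25 = 0.064 at 25% positive and 0.4·0.04 + 0.6·0.01 + 0.24·0.25 = 0.082 at 40%. Against 0.0856, k is about 1.15 and 1.02, so little is lost. The exposure lies in the groups of 10 against the controls.

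**The case against.** The strongest reply is that the protocol does not fix this error. Section 9.2 offers a list for continuous variables in general, and regression is on it. TBR is not mentioned there and no contrast is specified. Section 2.2.2 frames the Cohort 2 endpoint as presence and site of platelet activation, so a comparison of mean TBR is only implied by the design and the list. A statistical analysis plan could specify an unequal-variance test.

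Further points stand:
- The figure of over two thirds is a prevalence the sample can detect, not a forecast that one third will be negative. It covers two of the three groups of 10, not the iatrogenic one.
- Specificity concerns classification, not the SD of TBR, and the controls combine two kinds of patient.
- Regions of interest follow uptake (6.7) or thrombus on CT (9.2), so whether negative scans receive a TBR is unsettled.
- No intervals are planned. If a group of 10 had the same TBR distribution as the controls, the type I error would be correct.

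A reader might therefore infer something stronger: that Student's test is prescribed for TBR and that 95% intervals for every Cohort 2 contrast will be much too narrow. The documents do not support that, because the test is not tied to TBR, the contrast is implied, and the SDs are unknown.

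The objection does not remove the point. Pooled variance is what the protocol names, ordinary regression on group shares the fault, and greater spread in the smaller group is the likely case on the protocol's own account. This improves a stated method; it does not ask for missing detail.

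**Conclusion.** The point holds conditionally. If mean TBR or SUV in a group of 10 is compared with the 50 controls, and the group of 10 varies more, the named test overstates precision. The loss is small when positive scans are weakly separated from background and large when they are well separated, as the tables show. That whole range rests on assumed SDs and separations.

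The comparison of Cohort 1 with the controls is untouched. Whether a large difference is detected would usually not change: in the k = 2.9 rows the two tests differ by about 9 points of power. The practical harm is standard errors and p-values that look firmer than groups of 10 can support. This is a cheap improvement to secondary comparisons, not a threat to the main result.

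**What to change.** In section 9.2, for TBR and SUV comparisons involving the groups of 10, replace Student's t-test with Welch's unequal-variance t-test, or with regression using heteroscedasticity-robust standard errors in a small-sample form. Nothing else in the design has to change.

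The cost is a few words, wider intervals for the groups of 10, and lower nominal power there: 5 to 16 percentage points across the simulated mixtures, much of it power that the pooled test gains from a standard error that is too small.

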## 10 ADVERSE EVENTS

The Investigator, or a delegated researcher, is responsible for the detection and documentation of adverse events that may be related to participating in the study and that meet the criteria and definitions detailed below.

### 10.1 Definitions

An **adverse event** (AE) is an untoward medical occurrence in a study participant. An **adverse reaction** (AR), in the context of this study, is any untoward and unintended response which is related to any dose of iodinated contrast agent or PET tracer administered to that participant.

A **serious adverse reaction** (SAR) is any AR that:

- results in death of the clinical trial participant; is life threatening\*;
- requires in-patient hospitalisation or prolongation of existing hospitalisation;

- results in persistent or significant disability or incapacity;
- consists of a congenital anomaly or birth defect;
- results in any other significant medical event not meeting the criteria above.

A **suspected unexpected serious adverse reaction** (SUSAR) is any AR that is classified as serious and is suspected to be caused by the iodinated contrast agent, that it is not consistent with the information in PET tracer Investigator Brochure.

\*Life-threatening in the definition of an SAE or SAR refers to an event where the participant was at risk of death at the time of the event. It does not refer to an event which hypothetically might have caused death if it were more severe.

## 10.2 Identifying AEs and ARs

All AEs and ARs related to the imaging procedures will be identified from the time a PET/CT scan related procedure commences until 7 days after PET/CT scan completion.

## 10.3 Recording AEs and ARs

AEs will be recorded in the study CRF. There is no requirement to complete an additional AE form.

When an AE occurs, it is the responsibility of the Investigator to review all documentation (e.g. hospital notes, laboratory and diagnostic reports) related to the event. To the extent the CRF permits, the Investigator will record relevant safety information in the CRF.

Any adverse reaction (AR) to iodinated contrast or PET tracer that meets seriousness criteria (see section 10.1) will be recorded and reported in the study CRF and will also be recorded on an ACCORD SAE form, which will then be sent to the Sponsor via email ([contact]).

Pre-existing medical conditions (i.e. existed prior to informed consent) should be recorded as medical history and only recorded as AEs/ARs if medically judged to have unexpectedly worsened during the study. Events that are consistent with the expected progression of underlying disease should not be recorded as adverse events.

## 10.4 Assessment of AEs, SAEs, ARs, SARs and SUSARs

Seriousness, causality, severity and expectedness will be assessed by the PI. The Investigator is responsible for assessing each adverse event. The CI may not downgrade an event that has been assessed by an Investigator as a SAR or SUSAR, but can upgrade an AR, SAR or SUSAR if appropriate.

### 10.4.1 Assessment of causality

The Investigator will make an assessment of whether an AE is likely to be related to the administration of iodinated contrast or PET tracer (and therefore be considered an AR) according to the definitions below.

- Unrelated: Where an event is not considered to be related to the administration of iodinated contrast or PET tracer.
- Possibly Related: The nature of the event, the underlying medical condition, concomitant medication or temporal relationship make it possible that the AE has a causal relationship to the administration of iodinated contrast or PET tracer in this study.

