### **4.3 EXCLUSION CRITERIA**

- <18 years of age
- Takatsubo cardiomyopathy
- Myocarditis
- Renal failure (estimated glomerular filtration rate <30 mL/min/1.73 m^2)
- Woman of child-bearing potential who are pregnant or breastfeeding
- Known allergy or contraindication to iodinated contrast or radiotracer
- Patients unable to tolerate the supine position
- Patients unable to provide informed consent

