#### **10.4.2 Assessment of seriousness**

Subsequent to the assessment causality, the Investigator will make an assessment of seriousness as defined in Section 10.1

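### Sections 10 and 10.2 identify events related to the imaging procedures, but the causality scale and the sponsor-reporting route recognise only contrast or tracer as a cause

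*Protocol*

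**What the plan says.** **What must be identified.** Section 10 makes the investigator or a delegate "responsible for the detection and documentation of adverse events that may be related to participating in the study". Section 10.2 puts this in terms of the scan: "All AEs and ARs related to the imaging procedures will be identified from the time a PET/CT scan related procedure commences", ending 7 days after the scan is complete.

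**What counts as a reaction.** Under 10.1 an adverse reaction (AR) "is any untoward and unintended response which is related to any dose of iodinated contrast agent or PET tracer administered to that participant". An AR that meets a seriousness criterion is called a serious adverse reaction (SAR).

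**How cause is graded.** Section 10.4.1 has two categories. The first is "Unrelated: Where an event is not considered to be related to the administration of iodinated contrast or PET tracer". The second, *Possibly Related*, applies where it is possible that "the AE has a causal relationship to the administration of iodinated contrast or PET tracer in this study". There is no third category.

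**What follows from the grade.** Section 10.4.2 continues: "Subsequent to the assessment causality, the Investigator will make an assessment of seriousness as defined in Section 10.1". Under 10.3, adverse events are recorded in the CRF, and a serious AR to contrast or tracer also goes on an SAE form to the sponsor. Section 10.5 restricts onward reporting to SARs and SUSARs. It names contrast in one sentence, and contrast or tracer in the sentence that sets the 24-hour deadline. It also sends every serious adverse event, whatever its relation to the tracer, to the tracer supplier within two business days.

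**The concern.** The events to be identified form a wider set than the events the causality scale can describe. An event caused by the procedure itself, rather than by either injected agent, falls inside 10.2. Yet 10.4.1 gives no way to record that the study procedure caused it.

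The protocol treats tolerance of the procedure as relevant, since it excludes "Patients unable to tolerate the supine position". By section 6.7 the scan takes place within 7 days of symptom onset. It involves 60 minutes of rest after injection and two 20-minute bed positions, so 60 + 2 × 20 = 100 minutes before the CT angiogram.

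Two things are at stake. The safety record would label an event as unrelated when the investigator believes a study procedure caused it. And the sponsor would have no prompt notice of a serious event of that kind.

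**Working it through.** The point involves no figure of the plan, so the check is to follow one event through the text. Take a serious decompensation that the investigator attributes to supine positioning during the scan, with contrast and tracer both ruled out.

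1. **Section 10 and 10.2.** The event relates to participation and to the imaging procedure, and it falls within the time window. It must be identified.
2. **Section 10.3, recording.** It is entered in the CRF as an adverse event. No separate form is needed at this step.
3. **Section 10.4.1.** The only question is whether contrast or tracer administration may have caused it. The answer is no, so the grade is *Unrelated*.
4. **Section 10.1.** It is not related to a dose of either agent, so it is not an AR. SAR and SUSAR are both defined as kinds of AR, so it is neither.
5. **Section 10.4.2.** Seriousness is assessed against 10.1, where the criteria are attached to ARs. The heading of 10.4 and the footnote to 10.1 mention SAEs, but 10.1 does not define one.
6. **Section 10.3, SAE form.** The form goes to the sponsor for serious ARs to contrast or tracer. This event does not qualify.
7. **Section 10.5, sponsor.** The sentence that restricts onward reporting and the 24-hour trigger both require a SAR or SUSAR. This event does not qualify.
8. **Section 10.5, supplier.** The clause covering all serious adverse events does apply. The tracer supplier is told within two business days.

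Other provisions do not close the gap. The chief investigator's power to upgrade (10.4) lists AR, SAR and SUSAR, not an adverse event graded as unrelated. Severity is graded for SARs (10.4.3). Follow-up to resolution is required after a radiotracer-related SAR or SUSAR (10.7).

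Side by side, the scopes are:

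| Step | Section | Scope |
|---|---|---|
| Detect | 10 | Study participation |
| Identify | 10.2 | Imaging procedures |
| Define a reaction | 10.1 | Contrast or tracer |
| Grade cause | 10.4.1 | Contrast or tracer |
| SAE form to sponsor | 10.3 | Contrast or tracer |
| Report to sponsor | 10.5 | Contrast; then contrast or tracer |
| Report to supplier | 10.5 | All serious adverse events |

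The supplier is therefore informed of an event for which the protocol sets no report to the sponsor.

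**The case against.** **Narrow reporting is a deliberate choice.** Section 10.5 gives its reason: the study is a non-CTIMP and the risks of its procedures are well documented. Identifying widely and expediting narrowly is not in itself a contradiction. This stands as a reason for limited expedited reporting. It does not explain a causality scale that cannot register the relationship 10.2 sets out to identify.

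**The grade is literally correct.** *Unrelated* is defined against the two agents, and a purely procedural event meets that definition. This is true, but the record then cannot separate a procedure-caused event from one with no connection to the study.

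**Few events would take this path.** *Possibly Related* needs only that timing or the nature of the event makes a link possible. An arrhythmia on the scanner occurs about an hour after tracer injection, or close to contrast injection, so a link could often not be excluded. Cannulation or extravasation injury can be read as part of administration. This stands and limits the size of the point. A reader might infer that every serious on-scanner event would be graded as unrelated. The wording of 10.4.1 does not support that.

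**The event is not lost.** A reader might infer that it can never come to the sponsor's knowledge. It is in the CRF, and section 11.1 gives the sponsor direct access to records on monitoring or audit. Under 11.2, however, monitoring takes place only if considered necessary, and access to records is not a duty to report. One sentence in 10.5 on emailing the SAE form within 24 hours follows the supplier clause and could be read as covering every serious event. In context the form belongs to the SAR/SUSAR report.

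**No safety conclusion is planned.** A reader might fear that a count such as none in 80 would be presented as proof that the imaging is safe. The endpoints in 2.2 do not include safety, section 9.2 plans no safety rate, and procedural events in the CRF could still be tabulated. The documents do not support that stronger reading.

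**Conclusion.** The mismatch is real. Sections 10 and 10.2 cover study participation and the imaging procedures, while 10.1, 10.3, 10.4.1 and 10.5 recognise only contrast or tracer in classifying an event and reporting it to the sponsor. A serious event attributed to the PET/CT procedure alone is graded as unrelated, recorded in the CRF and given no route to the sponsor.

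The affected subset is serious events confidently attributed to the procedure with no possible link to either agent. It is probably small, and the protocol gives no rate from which to size it. Up to 50 + 10 + 10 + 10 = 80 participants are exposed. For an assumed true rate p of such events, the chance of at least one is 1 − (1 − p)^80:

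- p = 0.1%: 1 − 0.999^80 = 8%
- p = 1%: 1 − 0.99^80 = 55%
- p = 2%: 1 − 0.98^80 = 80%

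These rates are assumptions with no anchor in the document. The range shows only that the size is unknown, and the conclusion does not depend on it. No endpoint, sample size or planned analysis is affected. The point rests on reading 10.4.1 and 10.5 as written, with *administration* not stretched to include positioning or transfer.

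**What to change.** Give the sections one scope by adding *or any study-specific PET/CT procedure* in four places:

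- **10.1:** the AR definition. The SAR definition then follows without further edit.
- **10.4.1:** both causality categories.
- **10.3:** the sentence on which events go on the SAE form. It names contrast or tracer explicitly, so changing 10.1 and 10.4.1 alone would not reach it.
- **10.5:** the sentence restricting onward reporting and the sentence setting the 24-hour report, for the same reason. These two already differ on whether tracer is included, and should be brought into line in the same edit.

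The cost is a wording amendment, a change to one CRF field and possibly a few extra SAE forms. No visit, procedure or participant is added.
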